## **6 Study Procedures:**

CONFIDENTIAL

This material is the property of the NYU School of Medicine and Langone Medical Center. Do not disclose or use except as authorized in writing by the study sponsor

	Visit 1	Visit 2	Visit 3	Visit 4	Visit 5	Visit 6	Visit 7	Visit 8	Visit9	Visit 10	Visit 11
Study Procedures and Assessments	Week -3-0	Week 0	Week 1	Week 2	Week 3	Week 4	Week 6	Week 7	Week 8	Week 9	Week 10
	Screening	Baseline 1	Treatment (LDX or PBO) 1			EOT 1	End of PBO Washout/ Baseline2	Treatment (LDX or PBO) 2			EOT 2
SCREENING											
Consent	X										
Demographics	X										
M.I.N.I	X										
ACDS v1.2	X										
Medical History	X										
Psychiatric History	X										
Medical Review of Systems	X										
Physical Exam	X										
Hematology, Chemistry, Urinalysis, and UDS	X										
Urine Pregnancy Test	X										
ECG	X										
Review Eligibility	X	X	X								
EFFICACY											
ADHD-RS		X		X	X	X	X	X	X	X	X
Barkley SCT Scale		X		X	X	X	X	X	X	X	X
CGI-S		x		X	X	X	X	X	X	X	X
SAFETY											
Vital Signs		X	X	X	X	X	X	X	X	X	X
C-SSRS		X	X				X	X			X
Concomitant Medications		X	X	X	X	X	X	X	X	X	X
Adverse Events		X	X	X	X	X	X	X	X	X	X
NEUROPSYCHOLOGICAL BATTERY/EXECUTIVE FUNCTIONING											
CANTAB ADHD		x					X	X			X
WAIS-CODING & SYMBOL SEARCH		X					X	X			X
BRIEF-A		X					X	X			X
BFIS		X					X	X			X
ON-TOP		X									
OTHER											
Dose Dispense/ Adjustment			X	X	X	X			X	X	X
Drug Accountability				X	X	X	X	X	X	X	X

CONFIDENTIAL

This material is the property of the NYU School of Medicine and Langone Medical Center. Do not disclose or use except as authorized in writing by the study sponsor

**STUDY VISIT SCHEDULE:** This is a two part study. Patients will sign this consent form and be asked to do the following: Visit the study doctor weekly over a 12-week period, communicate over the phone between visits 6 and 7 and approximately 1 week after visit 10, and follow study instructions. In addition, patients who participate in the second part of the study will be asked to take study drug as instructed at the same time each day. Patient will have their blood drawn once in the study about 10mls will be collected for hematology and blood chemistry.

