**6.6 Visit 7 (Baseline 2) Day 42±2; Week 6**

Visit 7 will consist of ADHD-RS with prompts, Barkley SCT Scale, BRIEF-A, Barkley Functional Impairment Scale (BFIS), neuropsychological battery, CGI, vital signs, assessment of adverse events (AE) and concomitant medications (CM). Study Medication is dispensed. Drug accountability is performed.

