## 7.2 Statistical Methods

Phenotype Phase: Comparisons between the adult ADHD patients cohorts with SCT and without SCT in terms of ADHD symptoms (total, inattentive and hyperactive-impulsive, symptoms of executive function (BRIEF GEC, metacognition, behavioral regulation scales and subscales: Inhibit, Shift, Emotional Control, Initiate, Working Memory, Plan/Organize, Organization of Materials, Monitor), neuropsychological tests (CANTAB ADHD module, WAIS Coding and Symbol Search and Attention Network Test (ANT), and impairment (on Barkley Functional Impairment Scale (BFIS)) will be examine via One Way ANOVA .

Treatment Phase: Changes in outcome ratings in the patients in the treatment phase with LDX and placebo will be modeled with longitudinal generalized estimating equation (GEE) mixed regression models using STATA 12.0 [StataCorp, 2011 #25856] within the framework of the general linear model (GLM). The GLM allows us flexibility in modeling the outcome variable by choosing the appropriate distribution and link function. Each model will predict outcome scores from treatment group (drug vs. placebo), study visit (ordinal predictor), order (drug or placebo first) and the two and three-way interactions among: treatment group, visit, and order. We will first test for order effects and drop effects that are not significant at  $p < .05$ . The visit by treatment interaction indicates if the reduction in symptoms over time significantly differs between drug and placebo. Our primary analyses will be intention

CONFIDENTIAL

[SHIRE SCT s13-01288]  
Version: 03/03/2016

to treat (ITT) but we will explore the data with less conservative per protocol analyses to assure that we do not miss any signals in the data. Because this is a randomized trial, which follows subjects over a short period of time, missing data is not expected to impact our analyses. Should this become an issue, we will impute data using STATA's impute procedure. Using logistic regression, a responder analysis will be conducted using pre-hoc priori criteria for treatment response (30% decreases in total ADHD-RS and Barkley SCT scores). These will be last observation carried forward (LOCF) endpoint models that predict responder status (yes/no) from drug group, order and the drug by order interaction. Baseline symptom scores will be included as covariates.

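### The responder and adverse-event models use two records per crossover patient, but the plan states no patient clustering for either

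*Combined protocol and SAP*

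**What the plan says.** The Treatment Phase text of Section 7.2 models the outcome ratings with GEE. The predictors are treatment, "study visit (ordinal predictor), order (drug or placebo first) and the two and three-way interactions among: treatment group, visit, and order". The drug effect is read from visit by treatment: "The visit by treatment interaction indicates if the reduction in symptoms over time significantly differs between drug and placebo".

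The responder analysis follows in the same section: "Using logistic regression, a responder analysis will be conducted". A responder has a 30% fall in total ADHD-RS and Barkley SCT scores. The models are last-observation-carried-forward endpoint models that "predict responder status (yes/no) from drug group, order and the drug by order interaction", and "Baseline symptom scores will be included as covariates".

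The Safety Analysis paragraph of Section 7.2 tests adverse events with a general linear model, again on carried-forward endpoints with drug, order and drug by order.

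GEE is named for the ratings only. For the responder and adverse-event models the plan mentions no clustering, random patient effect or conditional model.

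**The concern.** Every patient who reaches the second block has one endpoint on LDX and one on placebo. A model with drug, order and drug by order has four cells (two orders by two treatments). All four are filled only if both blocks are used, because within a single block drug and order coincide. The two records from one patient are likely to be correlated.

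Ordinary logistic regression, fitted as the words stand, treats those records as independent. The drug comparison is made within patients, so positive correlation makes its standard error too large. The order comparison is made between patients, so its standard error is too small. The trial would give up part of the precision that the crossover provides on response, and could report an order effect that is not there.

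**Working it through.** **The plan's own figure.** Section 3.1 gives 80% power for 45 evaluable patients at effect size 0.6, two-sided 0.05. Φ(0.6·√(45/2) − 1.96) = Φ(0.886) = 81.2%, so the figure reproduces as a comparison of 45 with 45 records. It concerns the Barkley SCT score. No figure is given for the responder or adverse-event models.

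**Inputs.**
- Patients: 44, the number expected to finish washout (Section 3.1). Taken as 22 per order, an assumption, since Section 5.3 states block randomization but no ratio.
- Response 60% on LDX and 35% on placebo: assumed.
- Latent within-patient correlation 0.3, 0.5, 0.7: assumed. For 60% v 35% these give correlations between the two yes/no responses of φ = 0.183, 0.308, 0.440. For 35% v 35% they give φ = 0.187, 0.325, 0.486.

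**Drug effect averaged over orders (log odds ratio).**
- d = ln(0.60/0.40) − ln(0.35/0.65) = 1.025.
- a = 1/(44·0.60·0.40) = 0.0947; b = 1/(44·0.35·0.65) = 0.0999.
- Standard error assuming independence: √(a + b) = 0.441.
- True standard error: √(a + b − 2φ√(ab)) = 0.399, 0.367, 0.330.
- Unclustered power: Φ((d − 1.96·0.441)/true SE). Clustered power: Φ(d/true SE − 1.96).

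| Latent correlation | Unclustered, formula | Clustered, formula | Unclustered, simulated | Clustered, simulated |
|---|---|---|---|---|
| 0.3 | 66% | 73% | 66.9% | 75.3% |
| 0.5 | 67% | 80% | 68.0% | 82.7% |
| 0.7 | 69% | 87% | 69.7% | 90.8% |

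The simulations used 40,000 runs. The simulated losses are 8.4, 14.7 and 21.1 points. They slightly exceed the formula's because the robust test itself rejects 5.5-5.7% under the null at this sample size.

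**Type I error, both rates 35%.**
- Drug, unclustered: 2Φ(−1.96/√(1 − φ)) = 3.0%, 1.7%, 0.6%. Simulated: 2.9%, 1.6%, 0.5%.
- Order, unclustered: 2Φ(−1.96/√(1 + φ)) = 7.2%, 8.9%, 10.8%. Simulated: about 7%, 9%, 10%.

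**Sensitivity.**
- Zero correlation: about 65% v 66% power, almost no difference.
- With the planned baseline covariate (assumed correlation 0.3 with the outcome; 3,000 runs): 71.6/73.8/75.3% unclustered v 75.0/83.3/91.5% clustered, a loss of 3.4, 9.5 and 16.2 points. Unclustered type I error for drug is 4.5/2.2/0.9%.
- 55% v 35% response: 46.5% to 56.5% at correlation 0.3, and 45.2% to 75.0% at 0.7 (unclustered to clustered).
- 65% v 35% response: 83.2% to 88.7% at 0.3, and 87.5% to 97.6% at 0.7.
- With the 40 patients whom Section 3.1 expects to complete each treatment phase, standard errors rise by √(44/40) = 1.049. At correlation 0.5 the formula then gives Φ((1.025 − 1.96·0.463)/0.385) = 62% v Φ(1.025/0.385 − 1.96) = 76%, much the same gap.

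The adverse-event model was not computed. It has the same terms and the same pairing of records.

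**The case against.** **The GEE framework may be meant to cover the responder model.** The same paragraph sets up GEE and says that the framework leaves the distribution and link to be chosen. Logistic regression is the binomial, logit case, so a careful analyst could well fit it as GEE. That reading is possible, but it is not stated. The text names GEE for the ratings and then names plain logistic regression for response.

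**The harm is limited.** Response is not among the endpoints in Sections 3.2 and 3.3. For drug the error is on the conservative side, the baseline covariate reduces it, and the correlation is unknown. All of this stands and limits the weight of the point. But calling the unclustered analysis simply conservative would be wrong, because the order test errs the other way.

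**A stronger reading.** A reader might infer that the primary rating analysis is also compromised. Section 7.2 does not say whether visit is numbered within block. The schedule numbers visits through the study ("Visit 7 (Baseline 2) Day 42±2; Week 6"), and the plan says "We will first test for order effects and drop effects that are not significant at" the 0.05 level. The documents do not support that inference:
- Section 3.1 defines the powered change within a treatment block, and the schedule labels Visit 7 "End of PBO Washout/ Baseline2". Numbering within block is therefore the natural reading.
- With visit as a linear score across the study, a true weekly slope difference of −0.300 is still recovered as −0.300 if order is kept even as a main effect. It shrinks only when every order term is forced out. Under the plan's own dropping rule, the simulated mean effect was −0.147 to −0.150 for a true −0.150.
- With visit as categories across the study, the full model has 40 columns and rank 20. It cannot be fitted in full, which would send the analyst to within-block numbering.
- Large type I errors arise only if a one-order coefficient is read under 0/1 coding. The plan states no such coding. With the order-averaged contrast, the rule holds 5-6%.

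**Conclusion.** The point holds for the responder and adverse-event analyses. They require two records per patient, and the plan states no method for the pairing. The direction follows from the design for any positive within-patient correlation: the drug test is conservative and the order test anti-conservative. The sizes rest on assumed response rates and correlations. Over latent correlation 0.3 to 0.7 at 60% v 35%, the responder analysis loses roughly 8 to 21 points of power for drug, or 3 to 16 with the baseline covariate. The order test rejects about 7-11% under the null. At zero correlation the loss all but vanishes. No size is claimed for the adverse-event model.

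The point is worth fixing but concerns supporting analyses. Visit numbering and the order-averaged contrast in the primary model need a clarifying sentence. No harm is shown there under the plan's own rule.

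**What to change.** 1. In Section 7.2, state that the responder and adverse-event models account for the two records per patient, for example by logistic GEE clustered on patient with robust standard errors. Keep the baseline covariates in the responder model. A small-sample correction could be named, given the 5.5-5.7% null rejection above.
2. State that the reported drug effect is averaged with equal weight over the two orders. With drug by order in the model, a drug coefficient under 0/1 coding would describe one order only.
3. As a clarification, state that visit is numbered within block. State also that the primary contrast is LDX minus placebo in change from that block's baseline to its week 4, averaged over orders.
4. Reconcile the Visit 3 ratings. Section 6.3 lists ADHD-RS and the Barkley SCT Scale at Visits 3 to 5, but the Section 6 schedule table, as reproduced, shows no mark for either at Visit 3. Without Visit 3, a within-block model with five visit categories has rank 18 of 20.

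The cost is SAP wording and minor analysis work. No new data are needed.

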### 3 Study Design

#### 3.1 General Design

- 1) Total number of subjects/Total sample size: Approximately 120 patients with ADHD (with the final number of subjects depending on the proportion of ADHD subjects who have SCT; we have based our projections on an estimated 50% prevalence) in the phenotype phase (screening visit); 50 adults with ADHD and SCT+ will enter the treatment phase with LDX and placebo. We will analyze data from all subjects who take at least one dose of medication in both blocks. Using a 20% drop-out rate to occur throughout the trial, we estimate that approximately 50 subjects will enroll in the trial; 46 patients will complete the first phase of treatment, 44 patients will complete the intervening placebo washout, and 40 patients will complete each treatment phase.
- 2) Justification for sample size: We will enroll a sufficient number of subjects to recruit 80 patients with ADHD and SCT to enter the treatment study. The 50% prevalence of SCT in adult ADHD has been established in community samples [1, 2]. Power for this study was calculated using PASS [22] based on the primary outcome, i.e. change between baseline and week 4 of treatment on the Barkley SCT scale. Previous studies suggest that the upper bound of the effect size for the comparison of ADHD

CONFIDENTIAL

medications vs. placebo for ADHD symptoms varies between 1.2 and 1.5 standard deviations. Using a conservative estimate of effect that is half as robust for SCT as ADHD we based on our calculations on a 0.6 ES for SCT symptoms. The primary comparison will be a reduction in SCT symptoms on LDX vs. placebo. With 45 evaluable patients with SCT we will have 80% power to detect an effect size (ES) of 0.6 using a two-sided test with a type I error of 0.05.

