#### **8.5 Stopping Rules**

If subjects are experiencing a decline of 30% per the clinical assessments conducted they will be withdrawn. Patient experiencing adverse events that in the opinion of the investigator the subject can no longer participate due to a change in medical status (e.g. experiences from adverse events becomes pregnant the subject will be discontinued from the study).

These are the possible reasons for termination from the study:

- Adverse events
- Lack of efficacy
- Lost to follow-up

CONFIDENTIAL

This material is the property of the NYU School of Medicine and Langone Medical Center. Do not disclose or use except as authorized in writing by the study sponsor

- Pregnancy
- Withdrawal by subject
- Noncompliance
- Protocol violation
- Other

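### Section 7.2 treats missing data as harmless, against the plan's own 20% drop-out and assessment-based withdrawals, and its only fallback is an unspecified, post hoc imputation

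*Combined protocol and SAP*

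**What the plan says.** Section 7.2 (Treatment Phase) gives the premise: "Because this is a randomized trial, which follows subjects over a short period of time, missing data is not expected to impact our analyses". The only provision if the premise fails is "Should this become an issue, we will impute data using" Stata's imputation procedure. No trigger, imputation model, number of imputations, combining rule or sensitivity analysis follows. The outcome model is described as both GEE and mixed, with no working correlation or type of standard error. LOCF is specified for the responder and safety models, not for the main efficacy model. The primary analysis is intention to treat.

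Section 3.1 plans otherwise. It starts from "Using a 20% drop-out rate to occur throughout the trial, we estimate that approximately 50 subjects will enroll in the trial" and continues: "46 patients will complete the first phase of treatment, 44 patients will complete the intervening placebo washout, and 40 patients will complete each treatment phase". It also restricts the analysis to patients dosed in both blocks, a set that is not among the populations in section 7.3.

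Section 8.5 (and 8.4 in the same terms) says: "If subjects are experiencing a decline of 30% per the clinical assessments conducted they will be withdrawn". Section 8.5 also lists lack of efficacy and adverse events as reasons for termination.

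**The concern.** Randomisation balances the groups at entry and does nothing for exits that happen later for reasons linked to response or tolerability. A 10-week treatment trial is short, but the plan itself expects one patient in five to be gone by the end. Missing data are therefore expected, and some of the reasons for leaving plausibly track the ratings being analysed and may differ between LDX and placebo.

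Two things are at stake. First, ordinary GEE without weights needs exits to be unrelated to the ratings; otherwise the estimated LDX effect can be biased. Second, the fallback is invoked only after the data have been seen, so the result could influence which analysis is reported. It also leaves room for filling in the data once and counting imputed values as observed, which understates the standard error.

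**Working it through.** **The plan's own figures.** Section 3.1 sets a two-sided alpha of 0.05 and states: "With 45 evaluable patients with SCT we will have 80% power to detect an effect size (ES) of 0.6". With 45 per arm in a two-sample comparison, the noncentrality is 0.6 × √(45/2) = 2.85. The normal approximation gives Φ(2.85 − 1.96) = 81%; the noncentral t gives 80.4%. A paired test in 45 patients with within-patient correlation 0 gives 79.5%. The stated 80% is reproduced on these readings. It is not reproduced if 0.6 is the standardised paired difference (97.6%).

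Drop-out: 50 × 0.8 = 40, as stated. Missing at week 4: (50 − 46)/50 = 8% in block 1 and (50 − 40)/50 = 20% in block 2. On the readings that reproduce 80%, 40 completers give 74 to 75%; keeping 45 evaluable at 20% drop-out needs 45/0.8 = 56.25, so 57 enrolled.

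**Type I error of GEE under drop-out.** The documents give no SD, correlation or exit rate by treatment, so the following are assumptions: patient variance 0.40, period variance 0.15, AR(1) residual variance 0.45 (ρ 0.5), slope SD 0.15 (range 0 to 0.3), trend −0.15 SD per week. There are 50 patients, 25 per order, 5 visits per period and no drug effect. GEE uses independence or exchangeable correlation with robust standard errors. Drop-out is about 20% unless noted. Main scenarios used 4,000 to 6,000 runs, some sensitivity runs 3,000; Monte Carlo error is about 0.3 to 0.6 points. Rejection at nominal 5%:

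| Scenario | Drug × visit | Week 4 |
|---|---|---|
| No drop-out | 5.9% | 6.1% |
| Random drop-out (17%) | 5.4–5.6% | 5.9–6.0% |
| Rating-driven exits, same rule on drug and placebo | 5.3–6.3% | 5.7–6.1% |
| Rating-driven exits on placebo only, slope SD 0.15 | 8.3–8.6% | 8.8–9.7% |
| As above, slope SD 0 | 6.3% | 7.0–7.3% |
| As above, slope SD 0.3 | 12.1–14.3% | 12.2–13.8% |
| Placebo rating-driven plus random exits on drug (22%) | 6.0–6.5% | 6.7% |
| Placebo only (slope SD 0.15), restricted to patients dosed in both blocks | about 14.5% | about 12% |
| Single imputation, then GEE; same rule on both | 8.6–8.7% | 9.3% |
| Single imputation, then GEE; placebo-only exits | 8.4–10.2% | 9.2–10.1% |

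The roughly 6% with complete data is the small-sample level of the robust standard error. With placebo-only exits the bias is about 0.1 SD (0.05 to 0.25) against LDX, because the worst-rated placebo patients leave and the remaining placebo ratings look better.

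**Why single imputation inflates.** Take a paired test with 10 of 50 differences imputed once, and error variance σ².
- Mean imputation: reported SE = σ√0.8/√50, true SE = σ/√40, ratio 0.80. Rejection = 2 × [1 − Φ(1.96 × 0.80)] = 11.7%.
- Imputation with added noise: reported variance σ²/50 = 0.020σ², true variance σ²(1/40 + 10/50²) = 0.029σ², ratio √(0.020/0.029) = 0.83. Rejection = 2 × [1 − Φ(1.96 × 0.83)] = 10.4%.

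Regression imputation does somewhat better because it uses the patient's other ratings. With 4/50 and 10/50 missing at random (assumed patient SD 3, block response SD 4, residual SD 2; 6,000 replicates), a period-adjusted test rejected 5.0% with full data, 5.1% with complete cases and 8.9 to 9.0% after one imputation. Across three assumed variance sets, single imputation gave 8.6 to 10.1% and complete cases 4.6 to 6.0%.

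**Bias when the drug works.** With an assumed true effect of 3 points (about 0.6 SD of change) and 17 to 20% drop-out, three outcome-driven exit scenarios gave GEE errors of −2.2%, 0.0% and −3.2%. A likelihood mixed model gave −0.7%, +1.7% and −0.6%. Monte Carlo error is about 1 point. The largest GEE error is about 0.1 point (3.2% of 3).

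**The alternative under the null.** Generalised least squares with the true covariance, valid when exits depend on observed ratings, rejected drug × visit 5.4% (same rule on both), 5.0% (placebo only) and 4.6% (placebo only, slope SD 0.3), with bias within 0.005 SD. A fitted mixed model must estimate that covariance, so this is a best case.

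**The case against.** The strongest defence is that the practical damage from GEE looks small. The estimate was at most about 3% low and never overstated the benefit. With one exit rule applied in both periods, the test stayed at its complete-data level. In one of the three bias scenarios the mixed model was further from the truth than GEE. The word mixed in section 7.2 might even mean a likelihood model. On this evidence, changing the primary model is a matter of general validity more than demonstrated harm in every case. That stands, and it limits the severity.

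A reader might infer that GEE with assessment-based withdrawal by itself lifts the 5% test to about 9%. The documents do not support that. GEE alone reached such levels only when those exits occurred essentially on placebo only, and nothing in the plan says they will. In that case the bias runs against LDX, so the extra rejections mainly favour placebo.

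A reader might also infer that the plan prescribes single imputation. It does not: the number of imputations is simply absent, and properly combined multiple imputation fits the wording equally well.

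Nor do sections 8.4 and 8.5 state that exits depend on the Barkley SCT score. They name neither scale nor direction, while section 7.2 counts a 30% decrease in scores as response. Dependence on the outcome is plausible, not stated. None of this rescues the premise in section 7.2 or the undefined trigger.

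**Conclusion.** The point holds, as something that should be changed rather than a fatal flaw. The contradiction between section 7.2 and sections 3.1, 8.4 and 8.5 rests on the text alone, as does the absence of any usable missing-data rule for the main efficacy model. The missing fractions of 8% and 20% follow from the plan's own projection.

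The statistical size does not follow from the documents. Under the assumed variances above, GEE bias was 0 to 3%, and type I error was unaffected if exits act alike on both treatments and about 6 to 14% if they occur only on placebo. The 8.5 to 10% figure applies only if one imputed data set is analysed as real. Restricting to patients dosed in both blocks removes about 6 of 50 (those gone before block 2), conflicts with intention to treat, and made the placebo-only case worse.

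**What to change.** - Delete the sentence in section 7.2 and the conditional imputation trigger.
- Name the primary analysis as a likelihood-based linear mixed model, with patient and patient-by-block effects, on every observed rating of all randomised patients. It remains valid when exits depend on observed ratings.
- Replace the dosed-in-both-blocks set in section 3.1 so that it agrees with intention to treat in section 7.2 and the populations in section 7.3.
- Pre-specify multiple imputation (for example 50 sets, Rubin's rules) as a sensitivity analysis only. Add one missing-not-at-random analysis whose imputed values are defined by block and by treatment at exit.
- Reconcile the 30% decline in sections 8.4 and 8.5 with the 30% decrease used for response in section 7.2, as to scale and direction.

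The cost is SAP wording, a little code, and intervals slightly wider than single imputation would give. No new data are needed.

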### **1.1 Background**

SCT describes individuals who are “dreamy”, “spacey”, slow moving, hypoactive, have difficulty initiating tasks, and often seem under-motivated and under-aroused. In a population sample of 1,249 adults with and without ADHD, and with and without SCT, Barkley identified nine cardinal symptoms of SCT: 1) prone to daydreaming instead of concentrating; 2) trouble staying alert/awake in boring situations; 3) being easily confused; 4) being easily bored; 5) feeling spacey/in a fog; 6) frequently feeling lethargic; 7) being underactive/having less energy than others; 8) being slow moving; 9) not processing information quickly/accurately [1]. Individuals were identified as SCT if they had at least 5 of 9 symptoms rated often or very often on the 9-item SCT subscale from the Barkley Adult ADHD Rating Scale-IV: Self-Report (BAARS-IV; hereafter called the Barkley SCT Scale) [2]. The prevalence rate of SCT in this sample was 5.8%, approximately half of whom had ADHD. These results indicate that SCT is common in a large subgroup of adults with ADHD, but is not restricted to ADHD.

SCT may represent a clinically meaningful condition with distinct underlying pathophysiology and treatment response. Several investigators have posited the existence of neurobiologically distinct subtypes of ADHD that are differentially characterized by deficits in executive/inhibitory control, reward-related motivational processes, and state regulation [3-8]. This proposal to investigate treatment response of adults with ADHD and SCT is proposed in that context. To date, there has only been one naturalistic treatment trial of methylphenidate (MPH) in children with ADHD and SCT, which found that the response for SCT was lower than core ADHD symptoms [9].

However, that study was done with MPH. A controlled, clinical trial of LDX in adult ADHD with and without SCT is of critical importance for several reasons:

- 1) SCT is highly co-morbid and impairing in adult ADHD but there have been no controlled treatment studies of SCT in adults.
- 2) The magnitude of response in adults with ADHD and SCT is not known, but it is presumed (possibly incorrectly) from preliminary pediatric data that it may be less robust [9].
- 3) There have been no treatment trials of amphetamines (AMP) in SCT and ADHD.

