## **4 Subject Selection and Withdrawal**

### **4.1 Inclusion Criteria**

- 1) Male or female between the ages of 18-60 of all races and ethnicity.
- 2) Meets DSM-IV-TR criteria for a primary diagnosis of inattentive or combined type ADHD as diagnosed via the Adult ADHD Clinician Diagnostic Scale version 1.2 (ACDS v1.2) [10].
- 3) If SCT+ group,  $\geq 5$  items on the Barkley SCT Scale must be rated 3 ("often") or 4 ("very often") and total SCT symptom score  $\geq 26$ ; must have a T-score  $\geq 65$  on the Metacognition Index Subscale of the Behavior Rating Inventory of Executive Function - Adult Version (BRIEF-A) [11].
- 4) If SCT+ group, Impairment: must have a total score  $> 95$ th percentile on the Barkley Functional Impairment Rating Screen (Barkley Functional Impairment Scale (BFIS) [13].
- 5) If SCT- group,  $< 5$  items on the Barkley SCT Scale must be rated 3 ("often") or 4 ("very often") and total SCT symptom score  $< 26$ ; must have a T-score  $< 65$  on the Metacognition Index and Motivation Subscales of the BRIEF-A.

CONFIDENTIAL

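### LOCF in the responder analysis can count patients who leave a block early as responders; separately, what a 30% SCT drop means depends on a scale minimum the plan does not state

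*Combined protocol and SAP*

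**What the plan says.** Section 7.2 (Statistical Methods) adds a logistic-regression responder analysis to the GEE model of the scores. Response is defined by "pre-hoc priori criteria for treatment response (30% decreases in total ADHD-RS and Barkley SCT scores". On the endpoint it says "These will be last observation carried forward (LOCF) endpoint models that predict responder status (yes/no) from drug group, order and the drug by order interaction", and then "Baseline symptom scores will be included as covariates".

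Section 7.2 does not say:
- how a patient who leaves a block early is classified, other than through LOCF;
- whether a scale minimum is subtracted before the percentage is taken;
- whether the block 2 baseline is Visit 2 or Visit 7;
- whether response is needed on each scale separately or on both together.

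On the SCT scale, section 1.1 describes a case definition of "at least 5 of 9 symptoms rated often or very often on the 9-item SCT subscale". Section 4.1 gives codes 3 for often and 4 for very often and requires a total of at least 26 for the SCT+ group. No section gives the lowest item code or the range of the total.

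On exits, section 1.6.1 has the study doctor discontinue patients who develop any of a list of central nervous system effects, which includes dizziness, restlessness and headache. Section 8.5 lists both adverse events and lack of efficacy as reasons for termination. Section 3.1 expects 50 patients to enter, 46 to finish the first treatment block, 44 to finish the washout and 40 to finish both blocks.

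**The concern.** A responder rate is normally read as the share of patients who did well on the treatment. Under LOCF, a patient whose SCT total is 30% lower at week 2 and who then stops because the drug is not tolerated enters the week-4 analysis as a success. Because the plan provides for removing patients for stimulant effects whatever their symptom benefit, such cases are foreseeable. If they fall mainly in LDX blocks, the comparison is tilted towards LDX.

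The second issue is the percentage itself. On a scale whose lowest total is above zero, a 30% fall in the raw total is not a 30% fall in symptoms. If the SCT total cannot go below 9, the rule asks for more than its label suggests and asks the largest share of the patients who enter at the threshold. A reader who takes 30% at face value would then misjudge how many patients improved.

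**Working it through.** **The plan's own figure.** The plan states no responder rate and no power for the responder analysis. Its one computed figure is the 80% power in section 3.1 (45 evaluable patients, effect size 0.6, two-sided 0.05). As a comparison of two independent means with 45 per treatment, power = Φ(0.6 × √(45/2) − 1.96) = Φ(0.886) = 81.2%; the t-test version gives 80.4%. The figure reproduces and does not depend on the responder rule.

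**LOCF: how many patients it can reach.** Inputs are the section 3.1 attrition figures.
- Exits in block 1: 50 − 46 = 4 of 50.
- Exits in washout: 46 − 44 = 2. These patients have a week-4 score for block 1, so nothing is carried forward for that block.
- Exits in block 2: 44 − 40 = 4 of 44.

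The largest possible difference between LOCF and counting exits as non-response arises if every exit had already improved by 30%:

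| Setting | Calculation | Largest effect |
|---|---|---|
| Block 1, treatments pooled | 4/50 | 8 points |
| Block 2, treatments pooled | 4/44 | 9 points |
| LDX rate, every exit in both blocks on LDX | 8/47 | 17 points |
| LDX rate, half that number | 4/47 | about 9 points |
| Only patients dosed in both blocks analysed | 4/44 | 9 points |

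The 47 is (50 + 44)/2 LDX blocks started, assuming equal allocation to the two orders. The last row follows from section 3.1, which limits analysis to patients dosed in both blocks. If that is enforced, the four block 1 exits drop out and only the four block 2 exits can be carried forward. This conflicts with the intention-to-treat wording in 7.2 and the all-randomized population in 7.3.

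A carried-forward response also needs a rating after baseline. Section 6.3 has the SCT scale at Visits 3, 4 and 5, while the schedule table in section 6 shows none at Visit 3. That decides whether a patient who stops after Visit 3 has a post-baseline score to carry.

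**Scale minimum (assumption: nine items coded 1 to 4, total 9 to 36).** Raw rule: drop ≥ 0.30 × B. Minimum-adjusted rule: drop ≥ 0.30 × (B − 9).

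| Baseline B | Raw drop needed | Share of B − 9 | Adjusted drop needed |
|---|---|---|---|
| 26 | 7.8 (8 whole points) | 7.8/17 = 45.9% | 5.1 (6) |
| 30 | 9.0 (9) | 9/21 = 42.9% | 6.3 (7) |
| 36 | 10.8 (11) | 10.8/27 = 40.0% | 8.1 (9) |

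Illustration at baseline 30, with normally distributed change and an assumed SD of 6, using the whole-point cuts of 9 and 7:
- mean drop 6: P(drop ≥ 9) = 1 − Φ(0.50) = 31%; P(drop ≥ 7) = 1 − Φ(0.17) = 43%;
- mean drop 3: P(drop ≥ 9) = 1 − Φ(1.00) = 16%; P(drop ≥ 7) = 1 − Φ(0.67) = 25%.

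**Effect on the drug contrast.** A simulation used assumed inputs: baseline mean 28 to 32 with SD 3, limited to 26–36; SD of change 5 to 7; mean placebo drop 2 to 7; effect size 0.6. The raw rule lowered the responder rate by about 10 to 20 points in both treatments. The LDX/placebo odds ratio was 2.6 to 3.1 under the raw rule and 2.6 to 2.7 under the adjusted rule. The risk difference was 12 to 23 points (raw) against 19 to 24 (adjusted): usually smaller under the raw rule, but slightly larger when placebo change was large.

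**If items run 0 to 4.** The minimum is 0 and the two rules are identical.

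**Choice of baseline.** If Visit 7 is the block 2 baseline, the raw rule cannot be met from a total of 12 or less (0.7 × 12 = 8.4, below 9). The adjusted rule fails the other way: the denominator is zero at 9, and at 10, 11 or 12 a one-point drop is 100%, 50% or 33%. With the Visit 2 baseline the denominator is at least 26 − 9 = 17.

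**The case against.** The responder analysis is supplementary. It is not among the objectives in section 2 or the endpoints in 3.2 and 3.3, and neither the GEE analysis nor the power statement depends on it. That stands, and it limits the weight of the point.

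LOCF does not push only one way. Sections 8.4 and 8.5 withdraw patients whose clinical assessments decline by 30%, and 8.5 lists lack of efficacy. Such patients would ordinarily carry forward as non-responders, which is how they would be counted anyway. That stands too: the concern is confined to patients who improve and then leave.

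On the scale, a fixed 30% fall in the raw total is a legitimate, stricter bar applied equally to LDX and placebo. Nothing in the plan says that 30% was meant as a share of reducible points. This also stands.

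A reader might infer more than the documents support:
- That the minimum is 9. It is a reasonable inference from nine items and codes 3 and 4, but the lowest code is not given. Using the raw total is likewise the natural reading rather than a stated rule.
- That SCT benefit from LDX is understated. The lower responder rate applies to both treatments and the odds ratio hardly moves.
- That the rule would wrongly show SCT responding less than ADHD symptoms. Section 1.1 raises that question, but 7.2 plans no comparison of responder rates between the two scales, and the ADHD-RS range is not given either.

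**Conclusion.** The LOCF point holds on the documents alone. As written, 7.2 can count as a success a patient who improved and then stopped for intolerance. The effect is at most 8 to 9 points of the pooled responder rate per block on the plan's attrition, and smaller if some exits had not improved. The direction favours LDX only if LDX exits are mainly for intolerance, which the documents do not establish. A reader might take 17 points on LDX as the likely bias. It is an extreme bound that needs all eight in-block exits to be on LDX after early improvement, and it falls to about 9 points if only patients dosed in both blocks are analysed.

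The scale point is secondary and rests on 1-to-4 coding. If that holds, the raw rule asks for 40 to 46% of the reducible score and lowers the absolute SCT responder rate in both treatments, by 12 and 9 points in the two illustrations, which assume the SD and mean drops. If the minimum is 0, there is no effect. The two points work in opposite directions on the responder rate and should be handled separately. This is a cheap improvement to a supplementary analysis, not a threat to the primary one.

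**What to change.** In section 7.2:

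1. For the responder analysis, count a patient who leaves a block before its week-4 visit (Visit 6 or Visit 11) as a non-responder for that block. Keep LOCF as a sensitivity analysis.
2. State the Barkley SCT item coding and scale minimum. Report percent change on (score minus minimum) beside the raw version. Use the Visit 2 baseline as denominator, or another stated rule that avoids zero or very small denominators at Visit 7. If the minimum is 0, the two versions coincide.
3. Say whether response is required on each scale separately or on both.

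Two reconciliations decide who is affected: the both-blocks analysis set in 3.1 against 7.2 and 7.3, and the Visit 3 SCT rating in 6.3 against the schedule table.

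The cost is a few sentences and no new data, best settled before unblinding. Counting exits as non-response slightly lowers responder rates. The adjusted percentage is not directly comparable with studies that used the raw one, which is why both should be shown.
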